2.0 STUDY DESIGN

2.1 Nivolumab administration

Nivolumab will be administered at a flat dose of 240 mg IV infusion over 30 minutes +/- 10 minutes every 2 weeks for a maximum of 14 doses or 6 months duration. No premedications are required. If infusion reaction occurs, then premedications should be added with antihistamine, nonsteroidal anti-inflammatory drugs and/or steroids. Steroid therapy should be avoided if possible as premedication. The infusion should be given over 60-90 minutes +/- 10 minutes if infusion reaction occurs.

2.2 Radiation Therapy

Radiation Therapy (RT) needs to be started within +/- 3 days of nivolumab administration. Either therapy can be started first. RT would be administered at a total dose of 64 Gy in 32 fractions over a 6-8-week period in all patients. The RT can be done at any institution as it is Standard of Care and not covered by the study. The details of radiation therapy as required per protocol will be sent to the treating radiation oncologist.

SIMULATION

- Patient should be instructed to void prior to simulation for PTV40 to 46 Gy radiation course. Re-simulation with full bladder permissible for PTV64 Gy if bladder lesions can be visualized and adequately treated with daily IGRTCT simulation will be performed in the supine position with cradle immobilization recommended. Use of contrast is at the discretion of the treating radiation oncologist.

TECHNICAL FACTORS

- Radiotherapy will be delivered via linear accelerator with a minimum energy of 6 MV.
- Treatment will be delivered using either a three dimensional conformal approach (typically 3-4 field) or intensity modulated radiotherapy (IMRT) per institutional preference. Intensity modulated radiotherapy is only permissible if performed with daily CBCT or MVCT.

TREATMENT PLANNING

- Careful delineation of gross target volume (GTV_{BLADDER}) should be performed utilizing available imaging and bladder mapping to encompass all known areas of gross disease. For patients with radiographically or pathologically involved pelvic lymph nodes, a separate nodal GTV (GTV_{NODE}) should be defined.
- The clinical target volumes (CTV) will be delineated as follows:
 - CTV_{PRIMARY} = GTV_{BLADDER}
 - CTV_{BLADDER}: The entire bladder, including all gross intravesicular and extravesicular disease
 - CTV_{NODE} = GTV_{NODE}

- CTV_{PELVIS}: Inclusion of areas of potential microscopic spread, including external iliac, internal iliac, perivesical, presacral and obturator nodes, as well as, the prostate in male patients, is at the discretion of the treating physician. In the case of node positive disease, the pelvic lymph nodes should be included in the initial treatment field.

- The planning target volume (PTV) expansions are to be performed as follows:
 - PTV_{BLADDER}: 1.5 cm expansion around the bladder CTV
 - PTV_{NODE}: 0.5 to 1 cm expansion around radiographically or pathologically positive lymph node GTV
 - PTV_{PELVIS}: 0.5 to 1 cm expansion around the elective nodal CTV as defined above
 - PTV_{40 to 46 Gy} is a Boolean of PTV_{PELVIS} + PTV_{NODE} + PTV_{BLADDER} + PTV_{64 Gy} .
 - PTV_{54 to 60 Gy} is a Boolean of PTV_{NODE} + PTV_{64 Gy}
 - Adjustment of the PTV to meet dose constraints is allowable at the discretion of the treating radiation oncologist. *If the treatment course is to be delivered in more than one phase, it is necessary to generate separate planning target volumes (e.g. PTV_{BLADDER}, PTV_{NODE}, etc) utilizing the PTV expansions as delineated above.*
- The total PTV64 Gy dose delivered will be 64 Gy in 2 Gy per fraction.
 - 64 Gy Rx to cover at least 98% of PTV64 Gy
 - Minimum dose within PTV64 Gy – 95% of prescribed dose and for a volume that is 0.03 cc
 - Maximum dose within the PTV64 Gy – 110% of prescribed dose and for a volume that is 0.03 cc
- the initial phase of therapy will consist of a dose of 40 to 46 Gy delivered to PTVPELVIS, PTVNODE, and PTVBLADDER.
- The initial course of therapy should be delivered with an empty bladder and the boost should be delivered with a partial/full bladder.
- Radiation therapy may be delivered in up to three phases:

- o Treatment to the pelvic lymph nodes is recommended; the initial phase of therapy will consist of a dose of 40 to 46 Gy delivered to PTVPELVIS, PTVNODE, and PTVBLADDER. The initial course of therapy should be delivered with an empty bladder
- o The initial phase of therapy will consist of a dose of PTV40 to 46 Gy
 - 40-46 Gy Rx to cover at least 98% of PTV40 to 46 Gy
 - Minimum dose within PTV40 to 46 Gy – 95% of prescribed dose and for a volume that is 0.03 cc
 - Maximum dose within the PTV40 to 46 Gy – 110% of prescribed dose and for a volume that is 0.03 cc
- o For patients with positive nodal disease, a second phase of treatment will consist of a dose of 54 Gy to 60 Gy delivered to PTV54 to 60 Gy (Boolean of PTVNODE and PTV64 Gy.)
- o The final phase of treatment will consist of a total dose of 64 Gy delivered to PTV64 Gy. In cases where the bladder GTV is readily discernible and daily IGRT with CB imaging is utilized, a partial bladder boost (PTV 64 Gy) for the final 5 treatments (10 Gy) is permissible at the discretion of the treating radiation oncologist.
 - The total PTV_{64 Gy} delivered will be 64 Gy in 2 Gy per fraction.
 - o 64 Gy Rx to cover at least 98% of PTV_{64 Gy}
 - o Minimum dose within PTV_{64 Gy} – 95% of prescribed dose and for a volume that is 0.03 cc
 - o Maximum dose within the PTV_{64 Gy} – 110% of prescribed dose and for a volume that is 0.03 cc
 - Radiation therapy may be delivered in up to three phases:
 - o The initial course of therapy should be delivered with an empty bladder
 - o The initial phase of therapy will consist of a dose of PTV_{40 to 46 Gy}
 - 40-46 Gy Rx to cover at least 98% of PTV_{40 to 46 Gy}
 - Minimum dose within PTV_{40 to 46 Gy} – 95% of prescribed dose and for a volume that is 0.03 cc
 - Maximum dose within the PTV_{40 to 46 Gy} – 110% of prescribed dose and for a volume that is 0.03 cc
 - o For patients with positive nodal disease, a second phase of treatment will consist of a dose of 54 Gy to 60 Gy delivered to PTV_{54 to 60 Gy} (Boolean of PTVNODE and PTV_{64 Gy}.)

- The final phase of treatment will consist of a total dose of 64 Gy delivered to PTV_{64 Gy}. In cases where the bladder GTV is readily discernible and daily IGRT with CB imaging is utilized, a partial bladder boost (PTV_{64 Gy}) for the final 5 treatments (10 Gy) is permissible at the discretion of the treating radiation oncologist. In this case, the patient may undergo a re-simulation with a full bladder at the discretion of the treating radiation oncologist.

CRITICAL STRUCTURES

- Bladder, rectum and femoral heads should be defined as organs at risk (OAR). Rectum should be defined from the anorectal ring caudally to the rectosigmoid junction cranially. The following dose constraints should be met:
 - Rectum V30 <50%
 - Rectum V55 <10%
 - Femoral heads Maximum dose limit <45 Gy per RTOG 0926
 - Small bowel and sigmoid. V30<30%, maximum dose limit 50 Gy.

2.3 Study Calendar

Prestudy labs, physical exam and EKG should be done within 28 days of day 1. Day 1 labs can be done within 3 days of day 1. A window of +/- 3 days is permitted for the days of nivolumab therapy.

Testing	Pre study	Wk 1	Wk 3	Wk 5	Wk 7	Wk 9	Wk 11	Wk 13	Wks 15,17, 19,21, 23,25	6, 9 and 12 mths ⁴
H and P	X	X	X	X	X	X	X	X	X	X
VS, Wt	X	X	X	X	X	X	X	X	X	X
PS	X	X	X	X	X	X	X	X	X	X
Tox	X	X	X	X	X	X	X	X	X	X
Labs ¹	X	X	X	X	X	X	X	X	X	X
TSH, free T3/T4	X				X			X		X
ECG ²	X									
Cystoscopy ⁷	X							X		X

Biopsy ⁷	X							X		X
CT/MRI ³ of abdomen/pelvis	X							X		X
CXR/ chest CT ³	X									
Nivolumab		X	X	X	X	X	X	X	X	
visits during RT ⁵		X	X	X	X	X				
PFS/OS ⁶		X	X	X	X	X	X	X	X	X
Biomarkers ³	X				X			X		X
QOL questionnaires ³	X	X	X	X	X	X	X	X	X	X

1. Labs include: CBC diff, platelets, Electrolytes, BUN, creatinine, glucose, Albumin, alkaline phosphatase, total bilirubin, calcium, total protein, SGOT, SGPT. Pregnancy test for women of child bearing potential within 7 days of study enrollment and every 6 weeks thereafter.
2. ECG at screening and repeat if clinically indicated.
3. ICF, Baseline biomarkers, QOL questionnaires and all tumor evaluation/measurement scans must be within 42 days prior to treatment. CT/MRI of abdomen and pelvis is required for pretreatment and subsequent tumor assessments. CXR/CT chest is required at screening only to evaluate for metastases. Biomarkers should be collected at time of PD.
4. 6, 9 and 12 month visits will be from start of therapy. A window of +/- 28 days is permitted for these visits.
5. RT will be done **continuously** daily Monday to Friday (except for weekends and holidays) for a total of 32-35 fractions from week 1 to week 8. The time period of 8 weeks is a maximum duration as the radiation fractions can get delayed due to holidays, machine downtime, patient cancellation due to transportation etc. During RT patients should be evaluated for toxicity at a minimum every other week. Nivolumab should be started +/- 3 days of first day of RT.

6. After 12 months the patients will be followed for PFS and OS every 3 months for a maximum of 5 years.

7. Screening cystoscopy and biopsy can be performed within 6 months of day 1. On study cystoscopy will be done at week 13 and at months 6, 9 and 12 +/- 28 days. Biopsies will be required at week 13, month 6 and month 12 +/- 28 days. Month 9 biopsies done if clinically indicated.

The 6, 9 and 12 month timepoints for cystoscopy and biopsy (if needed) are to be followed for patients with no e/o malignancy in the bladder and no e/o metastases.

For patients requiring intra-vesical therapy for residual/new T1 or CIS in bladder, treatment will proceed as per standard of care and no specified timepoints will be followed. However, results of cystoscopy and biopsy should continue to be collected.

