1.6 Withdrawals

Subjects may discontinue study treatment or withdraw their consent to participate in the study at any time without prejudice. The investigator may withdraw a subject from study treatment or from the study if, in his or her clinical judgment, it is in the best interest of the subject or if the subject cannot comply with the protocol.

In addition, any of the following conditions require withdrawal of the subject from study treatment:

- An AE or intercurrent illness that in the opinion of the investigator warrants the subject's withdrawal from treatment
- Necessity for treatment with other investigational drug or other anticancer medications prohibited by protocol
- Participation in another clinical study using an investigational agent
- Request by regulatory agencies for termination of treatment of an individual subject or all subjects under this protocol
- Sexually active subjects who refuse to use medically accepted barrier methods of contraception (e.g., male condom, or diaphragm with spermicidal gel) during the course of the study and for 3 months following discontinuation of study treatment.
- Inability to tolerate nivolumab

- Nivolumab treatment delays greater than 6 weeks
- Progressive disease (PD) as determined by the investigator.

The reason for study treatment discontinuation will be documented. For subjects who discontinue or are withdrawn from study treatment, every effort must be made to undertake protocol-specified follow-up procedures and end-of-treatment assessments, if possible, unless consent for follow up in the study is also withdrawn.

If a subject fails to return for the protocol-defined visits, an effort must be made to determine the reason. If the subject cannot be reached by telephone, a registered letter should be sent to the subject (or the subject's legal guardian) requesting contact with the clinic.

If a subject is discontinued from study treatment because of an AE considered to be related to study treatment and the event is ongoing 30 days after the last dose of study treatment, the event must be followed until resolution or determination by the investigator that the event has become stable or irreversible.

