4.4 Laboratory Assessments

Local laboratories will perform all laboratory tests. Blood samples for standard hematology and serum chemistry will be done using standard procedures. Surveillance cystoscopies and biopsies as indicated are recommended every 3 months during the first 12 months after starting study therapy.

A cystoscopy and biopsy should be performed at any time prior to study entry, 13 weeks, 6 months, and 12 months after start of study treatment. At 9 months cystoscopy needs to be done and biopsies are done if clinically indicated and send archival slides if available. These assessments are considered standard of care and maybe delayed +/-28 days per

insurance requirements. Archival slides from pre-therapy biopsy and from week 13, 6 months, and 12 months need to be sent to:

[name].
Karmanos Cancer Institute
[name]
Correlative Sciences Lab Rm 808
[contact]
E-mail: [contact]

[name]
Karmanos Cancer Institute
[name]
Correlative Sciences Lab Rm 808
[contact]
Email: [contact]

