4.9 Progression-Free Survival (PFS)

PFS will be measured from treatment start date to date of first documented disease relapse/progression, or death from urothelial cancer whichever occurs first. If patients have residual invasive disease noted at cystoscopy and biopsy post therapy they are deemed to have disease progression at the time of the procedure. After treatment is discontinued/completed, patients will be followed every 3 months for progression and survival for a maximum of 5 years.

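### The two-sided 28-day window on the week-13 bladder biopsy lets the gap after radiation range from about 1 to 69 days, so the 12-month PFS rate may depend partly on scheduling; Section 4.9 must also define *post therapy*

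*Combined protocol and SAP*

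**What the plan says.** - **Biopsy timing.** Footnote 7 of Section 2.3: "Biopsies will be required at week 13, month 6 and month 12 +/- 28 days". Section 4.4 repeats the window for the 13-week procedure and gives its only reason, insurance requirements: "These assessments are considered standard of care and maybe delayed +/-28 days".
- **Radiation timing.** Footnote 5 of Section 2.3 plans RT "for a total of 32-35 fractions from week 1 to week 8" and adds: "The time period of 8 weeks is a maximum duration as the radiation fractions can get delayed".
- **Event rule.** Section 4.9 says of those found with "residual invasive disease noted at cystoscopy and biopsy post therapy they are deemed to have disease progression at the time of the procedure". There is no minimum interval after RT and no confirmatory biopsy.
- **After a positive biopsy.** The text closing Section 2.3 keeps only patients with a clear bladder and no metastases on the month 6, 9 and 12 cystoscopy and biopsy schedule. Section 4.3 moves patients who need other treatment for residual or progressive disease into follow-up.
- **Treatment period.** Section 4.2 ends it at the last dose of study treatment. Section 2.1 allows nivolumab for up to 14 doses or 6 months, so it is still being given at week 13.

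**The concern.** The calendar places the first bladder biopsy about four to six weeks after RT, but the early half of the window can remove up to 28 days of that. If tumour may still be clearing in those weeks, two patients with the same course could be scored differently: one biopsied early and counted as progressed, the other biopsied on or after the scheduled day and counted as progression-free. No scheduled repeat biopsy would correct the first result. The primary endpoint is the 12-month PFS rate in 30 evaluable patients, judged against a critical value of 0.64, so one or two such patients can decide the trial.

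**Working it through.** **1. The plan's own design figures reproduce.** Inputs from Sections 8.3 and 8.4.1: 12-month PFS 0.50 against 0.75, exponential times, accrual A = 24 and follow-up F = 12 months, one-sided alpha 0.025, power 0.95.

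- Hazards λ = −ln(p)/12: 0.0578 and 0.0240 per month.
- Event probability d = 1 − [exp(−λF) − exp(−λ(A+F))]/(λA): 0.7295 and 0.4297.
- Cube-root-hazard scale: N = [(1.96·λ0^(1/3)/(3√d0) + 1.645·λ1^(1/3)/(3√d1)) / (λ0^(1/3) − λ1^(1/3))]² = 29.9. With N = 30 the critical rate is 0.643 and power 0.951.

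This matches the stated 30, 0.64 and 0.95. The design calculation is not at fault.

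**2. Day count (treatment starts on day 1).**

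- Week 13 begins on day 1 + 7×12 = 85. Window: 85 − 28 = 57 to 85 + 28 = 113.
- Latest end of RT: end of week 8, day 56.
- Uninterrupted weekday RT from a Monday on day 1: 32 fractions end on day 44, 35 fractions on day 47. (Section 2.2 gives 32 fractions and footnote 5 gives 32 to 35. These need reconciling; both are used here.)

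| Case | Gap from end of RT to biopsy |
|---|---|
| Earliest biopsy, RT at 8-week maximum | 57 − 56 = 1 day |
| Earliest biopsy, 35 uninterrupted fractions | 57 − 47 = 10 days |
| Earliest biopsy, 32 uninterrupted fractions | 57 − 44 = 13 days |
| Biopsy on day 85 | 85 − 56 = 29 to 85 − 44 = 41 days |
| Latest biopsy, 32 uninterrupted fractions | 113 − 44 = 69 days |

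Section 4.4 counts 13 weeks from the start of treatment. Read as 13 full weeks, that is day 92. The window then opens on day 64, and the shortest gap after an 8-week course is 64 − 56 = 8 days.

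Section 2.2 lets RT start up to 3 days after nivolumab. A full 8 weeks from that start would end on about day 59, after the day-57 opening.

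**3. What *post therapy* could mean.** The close of Section 2.3 stops the scheduled biopsies for patients who are not clear, which fits a rule acting from week 13, that is, after RT. Section 4.2 points the other way: the post-treatment period begins only after the last dose, and nivolumab continues past week 13. On that reading a week-13 biopsy does not trigger the residual-disease rule. The text does not settle it.

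**4. Illustrative effect on the primary test.** Let m be the share of all patients counted as events only because they were biopsied early. The documents give no value for m. Assume a true rate of 0.75 and all 30 patients observed to month 12. Then 20/30 = 0.667 passes and 19/30 = 0.633 fails.

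| m | Observed rate 0.75 − m | Exact binomial P(X ≥ 20 of 30) | Exponential model, critical value 0.64 |
|---|---|---|---|
| 0 | 0.75 | 0.89 | 0.94 |
| 2.5% | 0.725 | 0.82 | 0.89 |
| 5% | 0.70 | 0.73 | 0.81 |
| 10% | 0.65 | 0.51 | 0.56 |

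The last column is Φ[(ln λc − ln λ)·√(30·d(λ))], with λc = −ln(0.64)/12, λ = −ln(0.75 − m)/12 and d as in step 1. It is approximate, because misclassified events would cluster at the biopsy date instead of following an exponential curve.

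**5. Direction.** Misclassification can only add events. It lowers the observed rate under the null as well, so type I error is not inflated.

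**The case against.** The opposing case is substantial, and much of it stands.

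- **One day is a corner case.** It needs RT at its maximum length, the earliest compliant biopsy day, and week 13 read as day 85. This stands. The other early cases, 8 to 13 days, are still well short of the scheduled interval.
- **The trigger is ambiguous.** This stands: Section 4.2 supports a reading under which the week-13 biopsy does not count under the residual-disease rule. That is itself a reason to amend Section 4.9.
- **Nothing shows that tumour is still regressing at these times.** This stands. A reader might infer that clearing tumour is being recorded as progression. The documents give no clearance rate, and Section 3.1 asks for maximal resection where feasible before entry, which may reduce the number affected.
- **Few biopsies may be early.** The stated reason for moving them is insurance delay, which pushes them later. This limits the likely size. It also means the early side of the window has no stated purpose.
- **Leaving treatment is not automatic.** A reader might infer that an early positive biopsy forces withdrawal. Section 1.6 requires "Progressive disease (PD) as determined by the investigator", and Section 4.3 names residual and progressive disease separately.
- **Discounting early positives would do harm.** This stands. With no scheduled repeat biopsy for such patients, true failures could be scored progression-free.
- **The month-12 window matters too.** At 365 ± 28 days it spans about day 337 to 393, so an event found there can fall on either side of the landmark. This is true, but a separate issue.

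**Conclusion.** The concern holds in limited form. The documents establish that the compliant gap from end of RT to the first on-study biopsy runs from about 1 to 69 days, that no minimum gap or confirmation is set, and that the early side of the window serves no stated purpose. If *post therapy* means after RT, the 12-month PFS rate depends partly on when the biopsy is booked, and any error lowers the rate.

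The size is unknown. The powers of 0.82, 0.73 and 0.51 are what-if values for assumed misclassification of 2.5%, 5% and 10%, not estimates. Nor should the 0.89 starting value be read as a shortfall from the planned 0.95 caused by biopsy timing: it arises from replacing the survival design with a binomial count, and the exponential model gives 0.94. The documents do not support a claim that the trial is underpowered or that its false-positive risk is raised on this account.

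**What to change.** 1. In footnote 7 of Section 2.3 and in Section 4.4, make the window for the week-13 cystoscopy and biopsy one-sided, 0 to +28 days. Insurance delay is still accommodated. On the day-85 reading the compliant gap narrows from 1–69 days to 29–69 days (85 − 56 to 113 − 44). The window remains tied to the start of treatment, so some variation stays.
2. In Section 4.9, state whether *post therapy* means after RT or after all study treatment, and reconcile this with the close of Section 2.3 and with Sections 4.2 and 4.3.
3. Do not add a rule that disregards residual invasive disease found before the week-13 date.

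The cost is a few sentences of protocol text and slightly less freedom to schedule early. Sample size and the analysis method are unchanged.

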3.0 STUDY POPULATION

3.1 Inclusion Criteria

- 1) Localized urothelial cancer of bladder with presence of transitional cell carcinoma (TCC) component. Mixed histologies are allowed.
- 2) Clinical or pathologic stage T2 –T4 disease including T4a and 4b if feasible to treat with radiation therapy.
- 3) Locoregional lymph node metastases are permitted but patients with distant metastases are ineligible. Imaging to evaluate for distant metastases should consist of a minimum of CT/MRI of abdomen/pelvis or CT urogram and a CXR or CT chest. Patients for which there is clinical suspicion or symptoms of bone metastasis should have a bone scan completed to rule out metastatic disease prior to enrollment on study.
- 4) Agreeable to consider radiation therapy (RT) for the urothelial cancer: patients have to be evaluated by a radiation oncologist and deemed to be candidates for RT.
- 5) The patients must not be candidates for chemotherapy due to at least one of the following reasons:
 - a. Performance status of 2
 - b. Creatinine clearance \leq 60 ml/min as calculated by the Cockcroft-Gault formula.
 - c. Cardiac disease such as NYHA Class III or IV heart failure or cardiac ischemia within the last 12 months, grade 2 or greater neuropathy, or other

comorbidities based on which patient is not considered a candidate for chemotherapy.

- 6) Adequate liver function with alkaline phosphatase, AST and ALT ≤ 3 x upper limit of normal and bilirubin < 1.5 x ULN
- 7) Adequate Bone marrow function defined as absolute neutrophil count $\geq 1500/\text{mm}^3$ and hemoglobin ≥ 9 g/dL and platelets $\geq 100\text{K}/\text{mm}^3$.
- 8) PS of 0-2 by Zubrod score
- 9) Life expectancy of 12 months
- 10) Age ≥ 18 years of age
- 11) Willingness to sign informed consent
- 12) Patients cannot have active autoimmune disease or immunosuppressive conditions.
- 13) Serum creatinine ≤ 1.5 X institutional ULN or creatinine clearance > 40 ml/min as calculated by the Cockcroft-Gault formula.
- 14) In females with childbearing potential, or men with partners of child bearing potential, willingness to use adequate contraception during the treatment period and for a minimum duration of 5 months after last dose of nivolumab.
- 15) Maximal tumor resection has been performed as feasible.

